#### PROJECT SUMMARY

Trigeminal neurostimulation of the dorsal anterior mucosal surface of the tongue has been proposed to treat a variety of pathologies and to promote neuro-muscular coordination and rehabilitation.

ULFTENS dental can also be considered a form of trigeminal neurostimulation applied to the skin surface bilaterally at the level of the tragus. With the latter mode of administration, there are central effects that can be evidenced at the level of pupil size (7,8), on the descending circuits that modulate pain, probably also on the centers that control arousal (9) and autonomic response under stress conditions monitored by HRV (10). The sensory component of the tongue is particularly developed, and the tongue itself is involved through its senses in a more complex modulation of sensory afferents than the tragus area, The aim of our project is to evaluate and compare the effects on two parameters of Heart Rate Variability (Low frequency, LF and Root Mean square standard deviation, RMSSD) in healthy women after 30 minutes of trigeminal electrical stimulation with dental ULF-TENS at the level of the dorsal anterior surface of the lingual mucosa or at the level of the tragus.

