#### **METHODOLOGY**

The research protocol involves the following procedure: Patients will be randomly divided into cases (TUD group) and controls (tragus group)following an online randomization software. Recordings will be made in the morning, the patient will be made to lie on a medical examination chair for a total of 30 minutes. Patients in the TUD group will be given a stimulation device to be inserted on the dorsal mucosa of the tongue and connected to TENS, while the control group will have two electrodes placed at the level of the tragus and also connected to TENS. Sensors for assessing Heart rate variability using a photoplethysmograph will also

be placed on the index finger of the hands. The photoplethysmographic wave will assess two parameters of HRV: the Low Frequencies (LF) and RMSSD. For the first 6 minutes of recording, the photoplethysmographic wave of HRV in the absence of stimulation will be calculated, then both case and control groups will be activated stimulation with TENS at the level of the tongue and tragus respectively. HRV under stimulation for another 6 minutes will be re-evaluated again. Finally TENS will be turned offand HRV wave after stimulation will be evaluated for the last time.

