#### **Statistics**

**Descriptive Statistics:** 

Demographic and baseline characteristics will be summarized using means, standard deviations, medians, and interquartile ranges for continuous variables, and frequencies and percentages for categorical variables.

Primary Outcome Analysis:

The primary outcome will be analyzed using an independent t-test (or Mann-Whitney U test if data are not normally distributed) to compare the intervention and control groups. Changes from baseline to post-intervention will be analyzed using paired t-tests (or Wilcoxon signed-rank tests if data are not normally distributed) within each group.

Secondary Outcome Analysis:

If secondary outcomes are included, similar statistical methods will be applied as appropriate based on the type of data (e.g., chi-square tests for categorical outcomes, ANOVA for continuous outcomes with more than two groups).

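### The single primary outcome is not identified: LF and RMSSD are listed jointly, with no endpoint form, significance level, success rule or multiplicity correction for the between-arm test

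*Combined protocol and SAP*

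**What the plan says.** - **Analysis.** Statistics, Primary Outcome Analysis: "The primary outcome will be analyzed using an independent t-test", with a Mann-Whitney test if the data are not normal. The outcome is singular and unnamed, and no criterion for normality is given. Paired tests of change within each group follow under the same heading.
- **Parameters.** The Project Summary sets out to "evaluate and compare the effects on two parameters of Heart Rate Variability", LF and RMSSD. Methodology repeats the pair: "The photoplethysmographic wave will assess two parameters of HRV: the Low Frequencies (LF) and RMSSD". Neither section ranks them. Secondary outcomes are conditional and none is listed, so neither parameter is placed in that tier.
- **Recordings.** Methodology has three: a baseline ("For the first 6 minutes of recording, the photoplethysmographic wave of HRV in the absence of stimulation will be calculated"), one during stimulation ("HRV under stimulation for another 6 minutes will be re-evaluated again") and one afterwards ("HRV wave after stimulation will be evaluated for the last time"). The last has no stated length.
- **Not stated in the text supplied.** Significance level, sidedness, success rule, multiplicity correction, sample size, and whether the between-arm test uses later values or changes.

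**The concern.** Under Aims and Objectives, the hypothesis is that stimulation at the tongue differs from stimulation at the tragus, and its confirmation is linked to possible clinical use. Two parameters and two endpoint forms could each supply the test of that hypothesis, and nothing says which one decides it. A reader of the results could not tell whether a difference in LF alone, in RMSSD alone, or only in both was meant to confirm it. These rules have different error rates and different power. With the choice open, it could be made after the data are seen. The trial is open-label, so prior specification is an important protection.

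**Working it through.** The plan states no alpha, power or sample size, so there is no figure of its own to reproduce. All figures below assume two-sided 0.05 per test (|z| > 1.96), normal test statistics and, for the error rates unless noted, no true difference between arms. All correlations are assumed.

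**1. Either parameter counts, one fixed endpoint form.** If independent: 1 − 0.95² = 0.0975. For correlated statistics, the chance that at least one exceeds 1.96 in absolute value, by numerical integration:

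| LF–RMSSD correlation | Either significant |
|---|---|
| 0 | 9.75% |
| 0.5 | 9.1% |
| 0.7 | 8.3% |
| 0.9 | 7.0% |

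**2. Either parameter counts, as post value or as change.** For each parameter the change statistic is (post − baseline)/√(2(1 − r)), where r is the baseline–post correlation. Its correlation with the post statistic is √((1 − r)/2), which is 0.5 at r = 0.5 and 0.387 at r = 0.7. Simulating all four statistics gives about 12.6% (r = 0.5, LF–RMSSD correlation 0.9) to 17.8% (r = 0.7, LF–RMSSD correlation 0). As a spot check at r = 0.5 with independent parameters, each parameter alone gives 0.0907, so the total is 1 − (1 − 0.0907)² = 0.173, inside that range.

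**3. Both must be significant.** If neither parameter differs, the chance is 0.10 minus the either-significant rate: 0.10 − 0.0975 = 0.0025 if independent, and 0.10 − 0.0704 = 0.0296 at correlation 0.9. If one parameter truly differs strongly, the rate rises towards 5%. It never exceeds 5%.

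**4. Cost of Holm if only one parameter differs.** Power that is 80% at 0.05 becomes, at 0.025, 1 − Φ(2.241 − (1.960 + 0.842)) = 0.712. Familywise error under Holm is 0.0494 (independent) to 0.0362 (correlation 0.9).

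**5. Gain from baseline adjustment (large sample).** With equal variances at baseline and post, the variance of the arm difference is proportional to 1 for post values, 2(1 − r) for changes and 1 − r² for ANCOVA.

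| r | ANCOVA relative to post values, 1 − r² | ANCOVA relative to changes, (1 + r)/2 |
|---|---|---|
| 0.5 | 0.75 | 0.75 |
| 0.7 | 0.51 | 0.85 |

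**6. Timing.** The Project Summary refers to effects "in healthy women after 30 minutes of trigeminal electrical stimulation". Methodology says "the patient will be made to lie on a medical examination chair for a total of 30 minutes", of which the first 6 minutes are unstimulated. That leaves at most 30 − 6 = 24 minutes for stimulation and the final recording together. The two statements cannot both hold.

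**The case against.** The strongest reply is that the candidate set is small and public: exactly two parameters, with no secondary outcomes listed. The natural reading is that both will be tested and reported, so what is missing is a success rule and an alpha. That largely stands. Silent switching is possible but not shown, and a reader should not infer that the plan adopts a rule under which either parameter suffices. It writes no such rule, and its plural references to parameters fit a both-required rule at least as well.

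Expected Results mentions a parasympathetic effect, which might hint at one parameter. It goes on to speak of HRV parameters in the plural and links neither to the primary outcome.

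Three further inferences are tempting and not supported:
- That 9.75% is the worst case. It is the highest rate only once the endpoint form is fixed.
- That the during-stimulation recording adds further primary tests. No between-arm test of it is stated. The wording of the paired-test sentence points to the after-stimulation recording, although the between-arm sentence names no time point.
- That the paired tests are meant to show a site difference. The plan gives that comparison to the independent test and describes the paired tests as within-group.

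It is also fair to say that an unadjusted comparison of randomised groups is valid once its endpoint is named. ANCOVA is not needed for validity. It is recommended because it settles post value versus change and uses a baseline already recorded. Finally, the title page was not available, so the finding is limited to the text supplied. The analysis section should still identify the outcome that it tests.

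**Conclusion.** The point holds as a gap in specification that can change the trial's conclusion. The text does not fix the parameter, the endpoint form, the alpha or the success rule. The possible inflation is moderate with one endpoint form (7.0% to 9.75%) and larger if the form is also open (about 12.6% to 17.8%). There is none if both parameters are required. These rates rest on the assumed 0.05 and the assumed correlations. They show what the open choices could cost and are not error rates of a stated procedure. The central finding does not depend on them. It should be corrected before data are seen. The conflict over stimulation time is a separate inconsistency.

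**What to change.** Before data are seen:

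1. State a two-sided alpha. Name the after-stimulation recording as the primary time point and state its length. Make the during-stimulation comparison secondary.
2. Choose one rule: (a) one parameter, named by the investigators, is primary and the other is tested only if the first is significant; (b) both are co-equal with Holm; or (c) both are required, each at full alpha.
3. Replace the unadjusted test with ANCOVA of the after-stimulation value on the 6-minute baseline. Fix one transformation or a rank-based form in advance, and do not let a normality test choose it.
4. Label the within-group paired tests as descriptive.

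**Cost.** Protocol and SAP wording and slightly more analysis work, with no new patients or recordings. Under (a), the second parameter cannot support a claim alone. Under (b), 80% power falls to about 71% if only one parameter differs. Under (c), power is lower because both tests must succeed. ANCOVA offsets some of this through the variance reductions shown above. The reduction is smaller at r = 0.7 if change scores were what the investigators intended.

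Separately, reconcile the stimulation time in the Project Summary with the chair time and recording schedule in Methodology. Which duration is intended is for the investigators to state.

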### STUDY DESIGN.

This research is a randomized, open-label, parallel-group clinical trial (interventional study). The population examined will be patients, aged 18-30 years old female from the Department of Orthodontics at the University of L'Aquila. The study will be performed in the same department. Patients participating in the study will be selected according to the exclusion and inclusion criteria. The exclusion criteria are: presence of acute and/or chronic cardio-circulatory and respiratory disorders, metabolic and autonomic system disorders, intake of excitatory or inhibiting substances of the peripheral and central nervous system, presence of generalised anxiety and/or panic attacks or mood disorders. All female patients aged 18-30 years will be included in the study. The selected patients will be randomly divided into two groups by means of randomization software downloaded into a computer.

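### The primary between-arm test is chosen by the observed distribution, so the quantity estimated is not fixed in advance, and neither candidate test adjusts for the recorded baseline

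*Combined protocol and SAP*

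**What the plan says.** The Study design section describes two randomized, open-label parallel groups. The Methodology section names the measurements: "The photoplethysmographic wave will assess two parameters of HRV: the Low Frequencies (LF) and RMSSD". Each patient is first recorded without stimulation: "For the first 6 minutes of recording, the photoplethysmographic wave of HRV in the absence of stimulation will be calculated". Two later recordings follow, one with TENS on ("HRV under stimulation for another 6 minutes will be re-evaluated again") and one after it is switched off.

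Under Primary Outcome Analysis in the Statistics section, the between-arm rule is: "The primary outcome will be analyzed using an independent t-test (or Mann-Whitney U test if data are not normally distributed". Change is then handled arm by arm: "Changes from baseline to post-intervention will be analyzed using paired t-tests (or Wilcoxon signed-rank tests if data are not normally distributed) within each group".

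The section does not say:
- which normality test or cut-off decides the switch, or whether it is applied to raw values, changes or residuals, by arm or pooled;
- whether the between-arm test compares follow-up values or changes;
- which effect measure or interval is reported;
- which of LF and RMSSD, at which of the two later recordings, is the primary outcome.

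No between-arm analysis with the baseline as a covariate is planned.

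**The concern.** The trial asks how two stimulation sites compare. A t-test answers with a difference in means. A Mann-Whitney test answers with a comparison of ranks, that is, the probability that a patient in one arm exceeds a patient in the other. Under the stated rule, the sample decides which question is answered. One parameter could be reported as a mean difference and the other as a rank p-value, and the reader could not set the two side by side.

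The second part concerns information already collected. The unstimulated recording is the natural covariate for the comparison of arms, but the plan mentions it only for within-arm tests, which do not compare tongue with tragus. If HRV before and after is even moderately correlated within patients, leaving the baseline out of the between-arm comparison gives away power that costs nothing to recover.

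**Working it through.** **Inputs.** From the documents: two randomized arms, two parameters, one baseline recording and two later ones, and the switching rule. The plan states no sample size, power or alpha, so there is no figure to reproduce. Assumed for illustration: two-sided alpha 0.05, equal arms of 15 to 30, Shapiro-Wilk at 5% in each arm as the gate, normal or lognormal data, and baseline-to-follow-up correlation ρ of 0.3 to 0.8.

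**1. The two targets can disagree.** Take two lognormal distributions with equal log-means and log SDs of 0.9 and 0.4. Then P(Y₁ > Y₀) = 0.5, so the rank comparison shows no difference. The ratio of means is exp(0.9²/2) / exp(0.4²/2) = exp(0.325) = 1.38.

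**2. How often the test would switch.** This depends on the assumed skewness.
- Normal data: about 8–10% of trials.
- Lognormal, log SD 0.3, 20 per arm: about 44% on follow-up values and 22% on changes.
- Lognormal, log SD 0.6, follow-up values: about 75%, 88% and 98% with 15, 20 and 30 per arm.
- Lognormal, log SD 0.5–0.9, ρ 0.5–0.7, 20 per arm: 76–99% on follow-up values and about 41–90% on raw changes.

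**3. What the baseline is worth.** The variance of the between-arm comparison, relative to follow-up values alone, is 2(1 − ρ) for change scores and 1 − ρ² for a model with the baseline as covariate.

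| ρ | Change score | Baseline-adjusted |
|---|---|---|
| 0.3 | 1.40 | 0.91 |
| 0.5 | 1.00 | 0.75 |
| 0.7 | 0.60 | 0.51 |
| 0.8 | 0.40 | 0.36 |

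For an assumed standardized difference of 0.8 and 80% power, the normal approximation needs 25 per arm on follow-up values. Multiplying by 1 − ρ² and rounding up gives 23, 19, 13 and 9 at the four correlations.

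**4. Power with 20 per arm and a true effect of 0.6 log-SD.** By normal approximation on the log scale:
- Follow-up values only: 0.6 × √(20/2) = 1.897; Φ(1.897 − 1.960) = 0.47.
- Baseline-adjusted, ρ = 0.5: 1.897 / √0.75 = 2.191; Φ(0.231) = 0.59.
- Baseline-adjusted, ρ = 0.7: 1.897 / √0.51 = 2.657; Φ(0.697) = 0.76.

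Simulation (2,000 to 2,500 trials per scenario, log SD 0.5–0.9, ρ 0.5–0.7) agrees, with slightly lower values:
- switching rule on follow-up values: about 42–46%;
- switching rule on raw changes: about 40–65%;
- log-scale model with baseline: about 55–73%.

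**5. Where the gain comes from.** The switching rule on follow-up values was set against a fixed log-scale t-test on the same values. Power in four scenarios was 46 vs 47, 45 vs 46, 46 vs 49 and 43 vs 44%. Across the checks the switch alone costs about 0–3 points; the rest is baseline adjustment. A separate run (normal data, 20 per arm, shift 0.8 SD, ρ 0.7, 3,000 trials) shows the same. Power was 70% for the switching rule and also for the plain t-test on follow-up values, 87% for Mann-Whitney on changes and 93% for the baseline-adjusted model.

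**6. Type I error of the rule followed mechanically.** It was 4.5–5.3% with 3,000 trials per scenario, and about 4–6% in the smaller runs.

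**The case against.** The strongest reply is that the switch does little measurable harm. Error is near nominal, the power cost is at most a few points, and where data are so skewed that 99% of trials switch, the analysis is in effect always Mann-Whitney and the target hardly moves. All of that stands. It limits the first part of the point to an unfixed target and an unstated criterion.

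Four stronger readings are tempting, and the documents do not support them.
- *The fallback cannot use the baseline.* It can: Mann-Whitney may be run on changes, and the plan does not exclude this. The accurate limit is that it takes no covariate, and the independent t-test takes none either.
- *The rule inflates type I error.* A rate of about 6–8% per comparison appears only if both tests are run and the better one is reported. The plan does not propose that. It says the trial is open-label but nothing about whether the analyst is masked.
- *The switch causes the power loss.* It does not, as step 5 of the working shows.
- *The rank branch alone loses the effect estimate.* The plan names no estimate or interval for the t-test either, and a location-shift estimate can accompany Mann-Whitney.

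It is also fair to object that skewness is assumed here. The documents give no unit, scale or SD for LF or RMSSD.

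**Conclusion.** The point holds in this form. The primary between-arm quantity is left to the observed distribution and may differ between LF and RMSSD, and the planned comparison does not adjust for a baseline that the protocol already records. The first part follows from the text alone. The size of the second rests on assumptions. With 20 per arm, lognormal data, ρ of 0.5–0.7 and an effect of 0.6 log-SD, adjustment raises power to 55–73%, from 42–46% on follow-up values or 40–65% on raw changes. At ρ = 0.3 the gain would be small (relative variance 0.91). The plan as written is not invalid. This is a worthwhile, nearly free improvement.

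**What to change.** Replace both normality switches under Primary Outcome Analysis with one pre-specified between-arm analysis, applied to LF and RMSSD alike:
- Name the follow-up window, during or after stimulation. Without this the target stays open even when the switch is gone.
- Fit a linear model of the follow-up value on arm and baseline value. Use the log scale for both values if the parameter is recorded in positive absolute units.
- Report the tongue/tragus ratio with a two-sided 95% confidence interval, whatever a normality test shows. If a parameter is not on such a scale, report the adjusted mean difference instead.
- Keep Mann-Whitney on the change from baseline as a sensitivity analysis.
- Treat the within-arm tests ("paired t-tests (or Wilcoxon signed-rank tests if data are not normally distributed) within each group") as descriptive, again without the switch.

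The cost is a short rewrite of the section and a decision on the follow-up window. No extra patients or recordings are needed. The downside is that results appear as ratios rather than raw differences.

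### Within-arm paired tests sit under the primary analysis, but with both arms stimulated and the unstimulated recording always first they cannot separate stimulation from time at rest

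*Combined protocol and SAP*

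**What the plan says.** **Treatment and order (Methodology).** Every participant starts unstimulated: "For the first 6 minutes of recording, the photoplethysmographic wave of HRV in the absence of stimulation will be calculated". Stimulation follows in both arms: "then both case and control groups will be activated stimulation with TENS at the level of the tongue and tragus respectively". The last recording comes with the device off: "Finally TENS will be turned offand HRV wave after stimulation will be evaluated for the last time". The trial is parallel-group (Study Design). No sham arm, unstimulated arm or randomised order of periods is described.

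**Analysis (Statistics, Primary Outcome Analysis).** Two procedures share this heading. The first is an independent t-test, or Mann-Whitney test, between the groups. The second reads "Changes from baseline to post-intervention will be analyzed using paired t-tests", or Wilcoxon signed-rank tests, in each group separately. The section does not say which procedure decides the conclusion, or whether the post-intervention value is the recording during stimulation or the one after it.

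**Question.** Aims and Objectives asks whether tongue stimulation differs from tragus stimulation. Project Summary is broader: "evaluate and compare the effects on two parameters of Heart Rate Variability". Expected Results anticipates a parasympathetic effect with better HRV values and names no comparator.

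**Time at rest.** Methodology has "the patient will be made to lie on a medical examination chair for a total of 30 minutes", whereas Project Summary describes effects "in healthy women after 30 minutes of trigeminal electrical stimulation with dental ULF-TENS".

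**The concern.** A paired test asks whether HRV changed. It does not ask whether TENS changed it. A woman who lies in a chair through three consecutive recordings may show a change in HRV simply because she has been resting, and the plan has nothing to measure that change by itself.

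Two wrong conclusions become possible. First, a favourable paired result could be reported as an effect of stimulation. Expected Results invites this: if the improvement it anticipates is relative to the unstimulated state, the paired tests are the only planned analysis that appears to address it. Second, one arm may reach significance while the other does not, and this may be read as a difference between sites although the sites were never compared.

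Aims and Objectives says that a confirmed hypothesis could point to use in chronic, difficult cases, so a mistaken attribution would have consequences beyond this study.

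**Working it through.** **1. What each test estimates.** For arm k, write S_k for the stimulation effect and R for the effect of elapsed rest, taken as common to both arms.

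- Within an arm: E(post − baseline) = S_k + R. Nobody is left unstimulated and the order never varies, so R cannot be estimated separately.
- Between arms: (S_tongue + R) − (S_tragus + R) = S_tongue − S_tragus. The common drift cancels.

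This holds whether the post value is the stimulation recording or the final one, since both follow baseline. The final recording does not rescue the paired test. No analysis contrasts it with the stimulation recording, and carry-over and continued rest would still be mixed in such a contrast.

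**2. Inputs for an illustration.** The plan states no sample size, alpha, drift or SD of change, so there is no figure of its own to reproduce. Assumed here: S_k = 0 in both arms, two-sided alpha 0.05, one parameter, n = 15 / 20 / 30 per arm, and the same drift d in both arms, in units of the SD of the change.

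**3. Paired test in one arm, favourable direction.** p = P(T > t_crit), where T is non-central t with n − 1 degrees of freedom and non-centrality d√n. Example, n = 20 and d = 0.5: 0.5 × √20 = 2.236, t_crit = 2.093, p = 56.45%.

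| Drift d | n = 15 | n = 20 | n = 30 |
|---|---|---|---|
| 0 | 2.5% | 2.5% | 2.5% |
| 0.2 | 10.80% | 13.35% | 18.39% |
| 0.3 | 19.04% | 24.65% | 35.53% |
| 0.5 | 43.78% | 56.45% | 75.40% |
| −0.3 | 0.12% | 0.06% | 0.02% |

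Only drift in the favourable direction looks like improvement.

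**4. Exactly one arm favourably significant.** The arms are independent, so the probability is 2p(1 − p). Example, n = 20 and d = 0.5: 2 × 0.5645 × 0.4355 = 49.17%.

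| Drift d | n = 15 | n = 20 | n = 30 |
|---|---|---|---|
| 0 | 4.88% | 4.88% | 4.88% |
| 0.2 | 19.27% | 23.13% | 30.02% |
| 0.5 | 49.23% | 49.17% | 37.10% |

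In all these cases the two sites have identical effects.

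**5. Between-arm test under the same drift.** Simulation with 40,000 trials per cell, an assumed baseline-to-post correlation of 0.6 and drifts from −0.3 to 0.5 SD: the t-test on change rejects in 4.73–5.17% and ANCOVA in 4.69–5.32%.

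**6. Does baseline adjustment help?** Assume n = 20 per arm, correlation 0.6 and a true site difference of 0.7 SD of the post value. The effect relative to the residual SD is 0.7 for the post value alone, 0.7/√(2 × 0.4) = 0.78 for the change score, and 0.7/√(1 − 0.36) = 0.875 for ANCOVA. Power is about 58%, 67% and 76%.

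**The case against.** The strongest reply is that the trial's question is already answered properly. Aims and Objectives asks about tongue versus tragus, the between-group test is listed first, and it is the only test the plan ties directly to the primary outcome. The paired tests are a separate sentence, nothing says they will be used to claim efficacy, and Expected Results contains no decision rule. The harm then lies in possible misreporting, and the rates above rest on a drift that the documents do not give.

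Much of this is fair. The randomised comparison is sound against common drift, and the percentages are illustrations. A paired test that detects real drift has also not erred; the error comes when the change is attributed to TENS. In addition, the plan never says which direction of LF counts as improvement, so the favourable direction is undefined for one of its two parameters. What remains is that p-values unable to bear a causal reading are placed under the primary analysis without a label, next to an expectation that invites that reading.

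A second objection concerns ANCOVA. Methodology describes allocation and device placement before the recordings, so the baseline may be taken after randomisation with a different device in place in each arm. If the device itself shifted HRV persistently by 0.3 / 0.5 baseline SD (an assumption, not documented), then with n = 20 per arm, correlation 0.6 and no stimulation effect, ANCOVA would reject in about 7 / 11% of trials and the change-score test in about 5%. The caveat is worth recording. It does not favour an unadjusted comparison of post values, which would reject in about 34% at a 0.5 SD shift.

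**Conclusion.** The concern holds; it should be fixed. That the paired tests cannot isolate stimulation follows from the design alone and needs no assumed figure. The size of the harm is unknown because it depends on a drift the plan does not state. Under the assumptions above, a single arm looks favourably improved in 11–18% of trials at 0.2 SD drift and 44–75% at 0.5 SD, against 2.5% with no drift. The design supports a conclusion about tongue versus tragus, and none about stimulation versus no stimulation.

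The argument does not depend on how long participants rest. Even so, 30 minutes of stimulation (Project Summary) and 30 minutes in the chair in total, starting with 6 unstimulated minutes (Methodology), cannot both hold in one session, since 30 − 6 leaves at most 24. The two sections must be reconciled.

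**What to change.** **Statistics, Primary Outcome Analysis**

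- Make the tongue-versus-tragus comparison, adjusted for the recorded baseline by ANCOVA, the sole basis for the primary conclusion.
- State in advance which recording supplies the post value.
- State when baseline is recorded relative to allocation and device placement. If the device is already in place, add the change-score comparison as a sensitivity analysis.
- Replace the Mann-Whitney fallback with a stated baseline-adjusted counterpart.
- Label within-arm changes descriptive, do not attribute them to stimulation, and do not compare significance in one arm with significance in the other.
- The plan records "two parameters of HRV: the Low Frequencies (LF) and RMSSD" but names neither as primary. Choose one, or state a multiplicity rule. If both were tested between arms at 5% and either sufficed, the error would be 1 − 0.95² = 9.75% if independent, and about 9.1 / 8.3 / 6.9% at correlations of 0.5 / 0.7 / 0.9. This is a secondary point and the main change stands without it.

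**Expected Results**

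- State the expectation as a difference between tongue and tragus, and say that an effect against no stimulation cannot be concluded from this design.

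**Cost.** These are wording changes in two sections, plus a clarification of baseline timing. The baseline is already recorded, and no extra arm, participants or visits are needed. The sponsor gives up any before-after statement of efficacy. If both arms change equally, the trial can report only that no difference between sites was shown.
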